2.4.2 Prior or concomitant medications

Double-blind period

The prior, concomitant and post-treatment medications will be presented for the safety population. Medications will be summarized according to the WHO-DD dictionary, considering the first digit of the anatomical therapeutic chemical (ATC) class (anatomic category) and the first 3 digits of the ATC class (therapeutic category). All ATC codes corresponding to a medication will be summarized, and patients will be counted once in each ATC category (anatomic or therapeutic) linked to the medication. Therefore, patients may be counted in several categories for the same medication.

The table for prior medications will be sorted by decreasing frequency of ATC followed by therapeutic class based on the overall incidence across treatment groups. In case of equal frequency across anatomic or therapeutic categories, alphabetical order will be used.

The tables for concomitant and post-treatment medications will be sorted by decreasing frequency of ATC followed by therapeutic class based on the incidence in the combined alirocumab group. In case of equal frequency across anatomic or therapeutic categories, alphabetical order will be used.

In addition, concomitant LMT medications will be summarized by pre-specified categories, chemical class or therapeutic class and standardized medication name.

OL period

All concomitant and post-treatment medications recorded during the OL period will be summarized in the OL population according to the WHO-DD dictionary.

2.4.3 Extent of investigational medicinal product exposure and compliance

The extent of IMP exposure and compliance for the double-blind period will be assessed and summarized for the safety population; for the OL period, it will be assessed on the OL population.

In addition, a description will be performed distinguishing patients with trial impact due to COVID-19 from those who were not.

2.4.3.1 Extent of investigational medicinal product exposure

Double-blind period

• Q2W dosing regimen cohort

The exposure during the double-blind period will be assessed using descriptive statistics for:

- The total number of double-blind IMP administrations by patient.
- Duration of IMP exposure in weeks defined as (last dose of double-blind IMP injection date first dose of double-blind IMP injection date + 14 days)/7, regardless of unplanned intermittent discontinuations (see Section 2.5.3 for calculation in case of missing or incomplete data).
- Q4W dosing regimen cohort

The exposure during the double-blind period will be assessed using descriptive statistics for:

- The total number of double-blind IMP administrations by patient.
- Duration of IMP exposure in weeks defined as:
 - (last dose of double-blind IMP injection date first dose of double-blind IMP injection date + 28 days)/7, for patients who stopped definitively the IMP before the switch to Q2W regimen (actual or sham) at Week 12, regardless of unplanned intermittent discontinuations (see Section 2.5.3 for calculation in case of missing or incomplete data).
 - (last dose of double-blind IMP injection date first dose of double-blind IMP injection date + 14 days)/7, otherwise, regardless of unplanned intermittent discontinuations (see Section 2.5.3 for calculation in case of missing or incomplete data).

Non-integer values will be rounded to one decimal place.

All quantitative parameters above will be summarized using number, mean, SD, median, minimum and maximum. In addition, the durations of treatment exposure will be summarized according to the following categories: ≥ 1 day and <4 weeks, ≥ 4 weeks and <8 weeks, ≥ 8 weeks and <12 weeks, ≥ 12 weeks and <16 weeks, ≥ 16 weeks and <22 weeks, ≥ 22 weeks.

OL period

• Q2W dosing regimen cohort

The duration of IMP exposure (in weeks) during the OL period will be defined as (last dose of open-label IMP injection date – first dose of open-label IMP injection date + 14 days)/7, regardless of unplanned intermittent discontinuations.

• Q4W dosing regimen cohort

The duration of IMP exposure (in weeks) during the OL period will be defined as:

- (last dose of open-label IMP injection date first dose of open-label IMP injection date + 28 days)/7, for patients still under Q4W regimen at the end of the open-label treatment period, regardless of unplanned intermittent discontinuations.
- (last dose of open-label IMP injection date first dose of open-label IMP injection date + 14 days)/7, otherwise, regardless of unplanned intermittent discontinuations.

Duration of IMP exposure will be summarized using number, mean, SD, median, minimum and maximum and according to the following categories: ≥ 1 day and ≤ 24 weeks, ≥ 24 weeks and ≤ 52 weeks, ≥ 52 weeks and ≤ 78 weeks, ≥ 78 weeks.

Combined period (double-blind and OL periods)

In each dosing regimen cohort, study treatment exposure variables combining double-blind and open-label periods are listed below for all patients who received alirocumab in the double-blind period and entered in the OL period:

- Combined duration of alirocumab exposure in weeks, regardless of unplanned intermittent discontinuations.
- The following categories will be used for treatment exposure intervals: ≥ 1 day and <24 weeks, ≥ 24 weeks and <52 weeks, ≥ 52 weeks and <78 weeks, ≥ 78 weeks and <102 weeks, ≥ 102 weeks.

Titration/dose-adjustment

For the double-blind period, the number and percentage of patients with an up-titration/doseadjustment in the alirocumab group during the double-blind period will be described for each dosing regimen cohort.

- In the Q2W dosing regimen cohort, patients with an up-titration are defined as up-titrated patients according to IVRS/IWRS Week 12 transaction with at least 1 injection of alirocumab 75 mg Q2W for patients with baseline BW<50 kg and 150 mg Q2W for patients with baseline BW≥50 kg afterwards.
- In the Q4W dosing regimen cohort, patients with a dose-adjustment are defined as doseadjusted patients according to IVRS/IWRS Week 12 transaction with at least 1 injection of alirocumab 75 mg Q2W for patients with baseline BW<50 kg and 150 mg Q2W for patients with baseline BW≥50 kg afterwards.

For the OL period, the number and percentage of patients with an up-titration/dose-adjustment at Week 32 or thereafter will be described for each dosing regimen cohort, as well as the number and percentage of patients down-titrated at least once. A summary of titration status will be provided by visit. Reasons for up- or down-titration and LDL-C used to up/down-titrate will be summarized, overall and by visit. LDL-C will be summarized quantitatively and with the following categories: <25, ≥ 25 and <50, ≥ 50 and <110, ≥ 110 and <130, ≥ 130 mg/dL.

2.4.3.2 Compliance

For the Q2W dosing regimen cohort, compliance for the double-blind period will be assessed using the following parameters:

- The mean administration frequency of IMP double-blind injections will be defined for each patient as the average number of days between 2 consecutive double-blind administrations, that is: (last double-blind administration date first double-blind administration date)/ (number of double-blind administrations -1) for patients receiving at least 2 administrations.
- The overall compliance for double-blind injections will be defined for each patient as: 100-(%days with under-planned dosing + %days with above-planned dosing). Under-planned and above-planned dosing will be defined as follows, considering that administrations should be performed every 2 weeks (±3 days as per protocol):
 - The % days with under-planned dosing will be defined for each patient as the number of days with no IMP administration within the previous 17 days divided by the duration of IMP exposure in days. For example, if a patient takes a dose 18 days after his/her previous administration, then 1 day is counted as a day under-planned dosing.
 - The % days with above-planned dosing will be defined for each patient as the number of days with more than one administration within the 11 days before divided by the duration of IMP exposure in days. For example, if a patient takes a dose 9 days after his/her previous administration, then 2 days are counted as days above-planned dosing.

For the Q4W dosing regimen cohort, compliance for the double-blind period will be assessed using the following parameters:

- The mean administration frequency of IMP double-blind injections will be defined for each patient as the average number of days between 2 consecutive double-blind administrations, that is: (last double-blind administration date first double-blind administration date)/ (number of double-blind administrations -1) for patients receiving at least 2 administrations.
- The overall compliance for double-blind injections will be defined for each patient as: 100-(% days with under-planned dosing + % days with above-planned dosing). Under-planned and above-planned dosing will be defined as follows, considering that administrations should be performed every 4 weeks (±3 days as per protocol) during the first 12 weeks and every 2 weeks (±3 days) afterwards:
 - The % days with under-planned dosing will be defined for each patient as:
 - the number of days with no IMP administration within the previous 31 days divided by the duration of IMP exposure in days, for the first 12 weeks.
 - the number of days with no IMP administration within the previous 17 days divided by the duration of IMP exposure in days, after the first 12 weeks.
 - The % days with above-planned dosing will be defined for each patient as:

- the number of days with more than one administration within the 25 days before divided by the duration of IMP exposure in days within the first 12 weeks.
- the number of days with more than one administration within the 11 days before divided by the duration of IMP exposure in days after the first 12 weeks.

If appropriate, for the Q4W dosing regimen cohort, mean administration frequency and compliance could be also provided separately for the first 12 weeks and the period after.

For the OL period, only mean administration frequency will be assessed for compliance.

• The mean administration frequency of IMP open-label injections will be defined for each patient as the average number of days between 2 consecutive open-label administrations, that is: (last open-label administration date – first open-label administration date)/(number of administration -1) for patients receiving at least 2 administrations (or partial administration)

These parameters will be summarized descriptively (N, Mean, SD, Median, Minimum and Maximum).

The percentage of patients whose overall compliance for injections is <80% will be also summarized as well as numbers and percentages of patients with 0%, >0% and \leq 5%, >5% and \leq 10%, >10% and \leq 20%, and >20% days with above-planned dosing and numbers and percentages of patients with 0%, >0% and \leq 5%, >5% and \leq 10%, >10% and \leq 20%, and >20% days with underplanned dosing.

According to protocol, cases of overdose are reported in the AE e-CRF pages and will be described in the AE analysis (see Section 2.1.4.1 and Section 2.4.5.1). More generally, dosing irregularities will be listed in Section 2.2.1.

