2.2 DISPOSITION OF PATIENTS

This section describes patient disposition for both patient study status and the patient analysis populations.

Screened patients are defined as any patient who signed the informed consent.

Randomized patients consist of all screened patients, with a double-blind treatment kit number allocated and recorded in the IVRS/IWRS database, regardless of whether the treatment kit was used or not. Patients treated without being randomized or treated with a double-blind treatment kit

before the randomization will not be considered as randomized and will not be included in any analysis population.

For patient study status in the double-blind period, the total number of patients in each of the following categories will be presented in the clinical study report using a flowchart diagram or summary table:

- Screened patients.
- Screen failure patients and reasons for screen failure.
- Non-randomized but treated patients, if any.
- Randomized patients.
- Randomized but not treated patients and reason for not being treated.
- Randomized and treated patients.
- Patients who completed the double-blind study treatment period as per protocol (as per eCRF end of double-blind treatment form).
- Patients who did not complete the double-blind study treatment period as per protocol (as per eCRF end of double-blind treatment form).
- Patients who discontinued the double-blind study treatment by main reason for permanent treatment discontinuation (as per eCRF end of double-blind treatment form).
- Status at last study contact for patients not entering in the open-label treatment extension.
- Patients participating in the open-label treatment extension period.

For all above categories of patients (except for the screened and non-randomized categories) percentages will be calculated using the number of randomized patients as denominator and summaries will be presented by treatment group as described in Section 2.4.

For patient study status in the open-label period, the total number of patients in each of the following categories will be presented in the clinical study report using a flowchart diagram or summary table:

- Patients treated during the OL period (all patients who received at least one open-label injection during the OL period).
- Patients who completed the OL treatment period as per protocol (as per eCRF end of openlabel treatment form).

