2.5 DATA HANDLING CONVENTIONS

2.5.1 General conventions

The following formulas will be used for computation of parameters:

Time from diagnosis of heFH

Time from diagnosis (years) = (Date of informed consent – Date of diagnosis*) / 365.25.

(*): In case the month of diagnosis would be missing, it will be put equal to 1st JANUARY if the year of diagnosis equals the year of informed consent; it will be put equal to 1st JUNE otherwise. In case only the day of diagnosis would be missing, it will be put equal to the 1st of the month.

Date of last dose of IMP (for double-blind and for open-Label)

The date of the last injection in the double-blind period is equal to the last date of administration reported on injection administration case report form page in double-blind period or missing if the last administration date is unknown.

The date of the last injection in the open-label period is equal to the last date of administration reported on injection administration case report form page in open-label period or missing if the last administration date is unknown.

Renal function formulas

Creatinine clearance value will be derived using the modified Schwartz equation presented in Appendix H.

Lipids variables, laboratory safety variables, Hs-CRP

For data below the lower limit of quantification (LLOQ) / limit of linearity, half of the lower limit value (ie, LLOQ/2) will be used for quantitative analyses. For data above the upper limit of quantification (ULOQ) / limit of linearity, the upper limit value (ie, ULOQ) will be used for quantitative analyses.

The above rules will not be applied for the calculated LDL-C and non-HDL-C when HDL-C value is below the LLOQ. The value of LLOQ/2 for HDL-C will be used to obtain the non-HDL-C and calculated LDL-C used for quantitative analyses.

Below is an example of data for a "dummy" patient, with the values that will be used in quantitative analyses for each parameter.

Parameter	Value recorded in the database	Value used in the analysis
TC	255 mg/dL	255 mg/dL
HDL-C	<10 mg/dL	5 mg/dL
Calculated LDL-C ^a	<221 mg/dL	216 mg/dL
NON-HDL-C	<255 mg/dL	250 mg/dL
TG	172 mg/dL	172 mg/dL

Table 4 - Example of lipid data for a "dummy" patient

a Friedewald formula for calculated LDL-C (when lipid expressed in mg/dL: LDL-C=NON-HDL-C-0.2*TG)

Pharmacokinetic variables

Data below the LLOQ are set to zero.

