 - Their open-label TEAE period, open-label treatment period and open-label on-study observation period will end at the cut-off date.
 - Their treatment duration for the open-label period will be derived by considering date of cut-off as last injection date.

- Open-label period: Analyses of number of injections, mean injection frequency, percentage of days with under/above-planned dosing and compliance will be performed up to the last injection reported in the e-CRF up to the cut-off date.
- Double-blind period and open-label period: AEs occurring, worsening or becoming serious after the cut-off date will not be included in the analyses. However, any available outcome before database lock, regardless of timing in relation to the cut-off date, of an adverse event starting prior to the cut-off date will be taken into account. Medications, treatment discontinuations/completions and deaths occurring after the cut-off date will not be included in the analyses.
- Open-label period: Post-treatment period and post-study period are not applicable for ongoing patients. Analyses of post-treatment AEs, post-study deaths and post-treatment medications will be performed for patients who either completed or prematurely discontinued the treatment before or at the cut-off date.
- Analysis of status at last study contact will be provided for patients who prematurely discontinued the study treatment before or at the cut-off date.

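### Double-blind compliance in the SAP cannot register doses skipped at the end of the period, so a patient who misses the last doses before Week 24 can score 100%

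*SAP*

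**What the plan says.** SAP 2.4.3.2 sets overall compliance at 100 minus the percentage of under-planned days minus the percentage of above-planned days. For the Q2W cohort, and for the Q4W cohort after Week 12, the under-planned percentage is "the number of days with no IMP administration within the previous 17 days divided by the duration of IMP exposure in days". Before Week 12 in the Q4W cohort the limit is 31 days in place of 17, over the same denominator. The share of patients below 80% overall compliance is to be tabulated.

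The denominator comes from SAP 2.4.3.1. For the Q2W cohort, exposure in weeks is (last double-blind injection date minus "first dose of double-blind IMP injection date + 14 days)/7, regardless of unplanned intermittent discontinuations". Q4W patients who reach the Week 12 switch get the same 14 days; those who stop definitively before it get 28. SAP 2.5.1 fixes the last injection as "the last date of administration reported on injection administration case report form page in double-blind period", that is, the last one given and not the last one planned.

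The other compliance measure, the mean number of days between administrations (SAP 2.4.3.2 and Protocol 11.4.1.2), also ends at the last administration.

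**The concern.** The time added after the last injection (14 or 28 days) is shorter than the gap needed before a day counts as under-planned (17 or 31 days). No day after the last injection can therefore count against the patient. A missed dose is penalised if a later dose follows it and ignored if none does.

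The omissions ignored are those closest to the Week 24 LDL-C sample. SAP Appendix C reports that in two Phase 2 studies mean LDL-C was back at baseline within 4 weeks of stopping alirocumab. On a strict Q2W schedule, a patient who skips only the final dose was last injected on Day 141, which is 28 days before the Day 169 target in SAP Table 5. A compliance table that shows this patient at 100% misdescribes adherence over the interval of most interest to a reader.

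**Working it through.** **Inputs.** Double-blind period of 24 weeks, or 168 days (SAP 1.1). Q2W dosing from Day 1 gives 12 doses, on Days 1, 15, …, 155. Under-planned limit 17 days (SAP 2.4.3.2). Exposure = last − first + 14 days (SAP 2.4.3.1). All doses not skipped are assumed to be on time.

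**The SAP's own examples.** An 18-day gap gives 18 − 17 = 1 under-planned day, and a 9-day gap gives 11 − 9 = 2 above-planned days. Both agree with the SAP.

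**Why terminal skips add nothing.** Let L be the last injection day. Exposure covers days up to L + 13. The first under-planned day is L + 18 (L + 17 if the 17-day window is taken to include the day itself). Both fall after exposure has closed. For Q4W patients who stop before Week 12, 28 < 31 gives the same result.

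**As written, last k doses skipped.**

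| k | L | Exposure | Under-planned days | Compliance | Mean interval |
|---|---|---|---|---|---|
| 1 | 141 | 154 days (22.0 wk) | 0 | 100% | 140/10 = 14.0 |
| 2 | 127 | 140 days (20.0 wk) | 0 | 100% | 126/9 = 14.0 |
| 3 | 113 | 126 days (18.0 wk) | 0 | 100% | 112/8 = 14.0 |

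**As written, k consecutive doses skipped in mid-course.** Exposure stays at 155 − 1 + 14 = 168 days. The gap is 14(k + 1) days, and the under-planned days are the gap minus 17.

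| k | Gap | Under-planned days | Compliance | Mean interval |
|---|---|---|---|---|
| 1 | 28 | 11/168 | 93.5% | 154/10 = 15.4 |
| 2 | 42 | 25/168 | 85.1% | 154/9 = 17.1 |
| 3 | 56 | 39/168 | 76.8% | 154/8 = 19.25 |

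**Terminal skips counted to Day 168.** Under-planned days run from L + 18 to 168, which is 151 − L: 10, 24 and 38 of 168. Compliance is 94.0%, 85.7% and 77.4%. If the window includes the day itself, the counts are 11, 25 and 39, giving 93.5%, 85.1% and 76.8%.

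**Q4W cohort.** With doses on Days 1, 29 and 57 and then every 14 days from Day 85 to Day 155, skipping the last 1, 2 or 3 leaves the same values of L. The results are the same: 100% as written, and 94.0%, 85.7% and 77.4% counted to Day 168.

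**Could the numerator run past exposure?** The SAP gives it no end date. Take a patient given only the doses on Days 1 and 15. Counting to Day 168 gives 168 − 32 = 136 under-planned days against an exposure of 15 − 1 + 14 = 28 days. Compliance would be 100 − 100 × 136/28 = −386%. Confining the numerator to the exposure window is the workable reading.

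**The case against.** The strongest reply is that nothing inferential depends on this. Compliance is summarised descriptively and enters no model, population or decision rule. The primary endpoint uses LDL-C regardless of adherence (SAP 2.1.3.1). That stands. A reader might infer that the compliance table is the plan's evidence that the Week 24 result reflects the assigned regimen, but neither document says so.

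Nor does the gap carry into the on-treatment analysis. SAP 2.4.4.2.1 keeps values up to 21 days after the last Q2W injection (the same for Q4W patients dosed beyond the Week 12 switch). With the last injection on Day 141 that is Day 162, while the Week 24 visit is planned for Day 168 ± 3 (Protocol 10.1.3.4), so Day 165 at the earliest. A value taken at that visit is already excluded. This also stands. It means the plan treats that sample as off-treatment while scoring the same patient as fully compliant.

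It can also be said that compliance describes regularity while on treatment, and that duration is reported elsewhere. This is partly true: two or three skipped final doses give 20 or 18 weeks and take the patient out of the top exposure category. One skipped dose gives exactly 22.0 weeks and stays in it, visible only in the number of administrations and the continuous duration. None of these tables corrects the percentage or the 80% flag.

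A reader might take the rule in SAP Section 3, which runs compliance up to the last reported injection, as further support. That rule covers the open-label period at the first-step cut-off and does not bear on double-blind compliance.

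**Conclusion.** The point holds as a defect in a descriptive measure. Three doses skipped at the end score 100%, against 76.8% for three consecutive doses skipped in mid-course and about 77% if the terminal gap is counted to Day 168. Timing alone decides which side of the 80% cut the patient falls on. One or two terminal skips overstate compliance by about 6 or 14 points without crossing the cut.

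The figures assume that every other dose was on time. More generally, terminal skips add zero under-planned days to whatever the patient has already accrued. The recount also assumes a Day 168 end, and the two readings of the 17-day window move it by about half a point. The documents give no expected frequency of terminal skips, so the effect on group means and on the share below 80% cannot be estimated. The ITT primary analysis, alpha and power are unaffected.

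**What to change.** Add one sentence to SAP 2.4.3.2. For patients recorded on the eCRF end-of-double-blind-treatment form as having completed the period (SAP 2.2), planned-dosing days are counted, and divided, over the days from the first double-blind injection to the earliest of Day 168, the Week 24 visit and the day before the first open-label injection. Patients who permanently discontinued keep the present exposure window, since their early stop is reported in the disposition tables. The same rule applies to the Q4W cohort, with its existing limits before and after Week 12.

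The cap matters. Without it, a patient with all 12 doses (last on Day 155) whose first open-label injection slipped to Day 182 would gain under-planned days 173 to 181, nine in all, with no dose missed. With the cap, that patient has none and the denominator is still 168 days.

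The cost is that sentence and minor programming. Protocol 11.4.1.2 lists only the mean injection interval, so no protocol change is needed. That interval will still not show terminal skips and is best read beside the number of administrations. Reported compliance may be slightly less favourable, and the rule relies on the completion form being filled in correctly.
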